### 8.2.28 Tapering of Corticosteroid Treatment

The week in which the tapering is initiated will be considered the start of tapering, this will be restricted to Study Period 1.

According to the CSP the taper regimen to be followed depends on the subject's previous stable corticosteroid dose:

CSP Section 5.3.2	Tapering at Week X+1, if
If stable dose is 11 to 20 mg/day oral prednisolone equivalent, decrease dose by 2.5 mg/day every 2 weeks, as tolerated, to 10 mg, then by 1 mg/day every 2 weeks as tolerated	$ADD_1 > 10$ and $ADD_X - ADD_{X+2} \geq 2.5$ and $ADD_{X+1} < ADD_X$ and $ADD_X \leq ADD_1$
If stable dose is $\leq 10$ mg/day, taper by 1 mg/day every 2 weeks as tolerated	$ADD_1 \leq 10$ and $ADD_X - ADD_{X+2} \geq 1$ and $ADD_{X+1} < ADD_X$ and $ADD_X \leq ADD_1$

ADDX: average daily corticosteroid dose in mg at Week X

Tapering after rescue corticosteroid treatment is defined as any reduction in the daily concomitant corticosteroid dose compared to the first day of rescue corticosteroid treatment.

### 8.2.29 Timed up and go

In case of multiple measurements per subject per visit the minimum result will be used. Analysis will be based on the following categories for timed up and go [Podsiadlo et al, 1991]:

- <10 seconds: completely independent
- $\geq 10 < 20$  seconds: independent for main transfers
- $\geq 20$  seconds: requires assistance

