#### 10.4.4 Exploratory Analyses

Pain/discomfort and Anxiety/depression domains of EQ-5D-5L, WPAI-GH, TSQM-9, Timed Up and Go, 5-D Itch Score, Muscle Enzyme, concomitant corticosteroid tapering, and ANA, MSA, and MAA will be described similarly to secondary efficacy endpoints as described in [Section 10.4.2.4.5](#). The observed values and changes from reference visits of these endpoints will be summarized by visit, and treatment sequence as appropriate.

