## Appendix 11 Timed Up and Go

### General

- The patient should sit on a standard armchair, placing his/her back against the chair and resting his/her arms chair's arms. Any assistive device used for walking should be nearby.
- Regular footwear and customary walking aids should be used.
- The patient should walk to a line that is 3 meters (9.8 feet) away, turn around at the line, walk back to the chair, and sit down.
- The test ends when the patient's buttocks touch the seat.
- Patients should be instructed to use a comfortable and safe walking speed. A stopwatch should be used to time the test (in seconds).

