### **5 Changes in the Conduct of Planned Analyses**

There were no changes to analyses planned in the study protocol.

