**Table 12: Exploratory Endpoints – Variables (Study Period 1 and Study Period 2)**

Endpoint	Variable	Type of summary measure
EQ-5D-5L	
 
• Pain/ discomfort
 
• Anxiety/ depression
 
	
 
• cumulative distribution function
 

	
 
• Utility index
 
• Health VAS
 
	
 
• continuous
 

WPAI-GH	
 
• Percent work time missed due to health
 
• Percent impairment while working due to health
 
• Percent overall work impairment due to health
 
• Percent activity impairment due to health
 
	
 
• continuous
 

TSQM-9	
 
• Effectiveness
 
• Convenience
 
• Global Satisfaction
 
• Item 1 to Item 9
 
 
Change from Baseline will not be summarized as there is no Baseline assessment for TSQM-9.
	
 
• continuous
 

Endpoint	Variable	Type of summary measure
Timed Up and Go	• Timed Up and Go	• categorical (see Section 8.2.29)
5-D Itch score	• Total score	• continuous
Muscle enzymes	Serum levels of • CK (IU/L) • LDH (IU/L) • AST (IU/L) • ALT (IU/L) • aldolase (IU/L)	• continuous
Serum IgG	• IgG serum concentrations	• continuous
	• IgG PK parameters $C_{max}$ , $C_{trough}$ , and AUC	• see Section 12
IIM autoimmune antibody panel	• MSA • MAA • ANA	• Response, categorical, continuous
HAQ	• Pain VAS	• continuous
MDAAT	• VAS Constitutional Disease Activity • VAS Cutaneous Disease Activity • VAS Skeletal Disease Activity • VAS Gastrointestinal Disease Activity • VAS Pulmonary Disease Activity • VAS Cardiovascular Disease Activity • VAS Other Disease Activity	• continuous
CDASI	• Total score • Total damage score	• continuous
Reduction of oral concomitant corticosteroid treatment	• Percent reduction of average daily dose	• continuous

The exploratory endpoints listed in Table 13 for Study Period 3 will be summarized descriptively only as described in Section 10.5. The data will be presented by sequence and overall including

visits from all 3 study periods based on the SAF-P3. Reference visits are described in Section 8.2.1.

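### Timed Up and Go is recorded in seconds and the protocol plans observed values and changes, but the SAP summarizes it only in three time bands, so within-band change will not show

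*SAP*

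**What the plan says.** Protocol 10.4.4 lists Timed Up and Go with the other exploratory endpoints and says: "The observed values and changes from reference visits of these endpoints will be summarized by visit, and treatment sequence as appropriate". Protocol Appendix 11 has the test timed by stopwatch in seconds. Protocol Section 8.5 schedules it at Baseline and Weeks 9, 17, 25, 33, 41 and 53, which makes seven visits.

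SAP 8.2.29 says: "Analysis will be based on the following categories for timed up and go". The bands are:

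- "<10 seconds: completely independent"
- 10 to below 20 "seconds: independent for main transfers"
- 20 or more "seconds: requires assistance"

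In SAP Table 12 the summary type for this endpoint is categorical, with a pointer to 8.2.29. There is no row for seconds or for change in seconds.

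SAP 10.6 sends the reader to 10.5 for methods. Section 10.5 describes continuous, TIS, time-to-event, response and cumulative-distribution summaries, but nothing for a three-level categorical variable. SAP Section 5 states: "There were no changes to analyses planned in the study protocol". The modification history for SAP version 4 does list a categorical analysis of Timed Up and Go.

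**The concern.** The protocol plans two summaries of a continuous measurement: its value at each visit and its change from the reference visit. The SAP replaces both with band membership and does not record the departure in the section meant for it.

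Bands this wide lose information in a predictable way. A fall from 18 to 11 seconds is no change; a fall from 10.1 to 9.9 seconds is an improvement. A subject who starts below 10 seconds has no better band to reach, and one at 20 seconds or more has no worse one. What is at stake is the resolution of one exploratory description, and the agreement of the two documents on it.

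**Working it through.** **The texts side by side**

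| Item | Protocol | SAP |
|---|---|---|
| Scale | Seconds (Appendix 11) | Three bands (8.2.29) |
| Summary | Observed values and changes (10.4.4) | Categorical only (Table 12) |
| Display of change | Change from reference visit | None defined for bands (10.5) |
| Departure declared | – | None (Section 5) |

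Table 12 is able to combine types: it gives the autoantibody panel response, categorical and continuous summaries together. Leaving seconds out is therefore not forced by the table's format.

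**What follows without any assumption**

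- Baseline below 10 seconds: improvement cannot show.
- Baseline of 20 seconds or more: worsening cannot show.
- Middle band: a gain shows only if it takes the subject below 10 seconds. A gain of more than 10 seconds always does.

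**How many subjects would be affected**

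The documents state no baseline mean, spread or expected change for this test, so there is no figure of theirs to reproduce. The following rests on assumed baselines.

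For a baseline time X and the same gain of d seconds in everyone (d below 10), the share that stays in its band is

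unchanged(d) = 1 − P(10 ≤ X < 10 + d) − P(20 ≤ X < 20 + d).

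*Uniform baseline on 5 to 30 seconds.* Each crossing interval has probability d/25, so unchanged(d) = 1 − 2d/25. For d = 2 this is 1 − 4/25 = 84%; for d = 5 it is 1 − 10/25 = 60%.

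*Lognormal baselines.* Medians of 7, 8, 9, 10, 11, 12, 15, 18 and 22 seconds were crossed with coefficients of variation (CV) of 0.15, 0.25 and 0.40, giving 27 scenarios of 400,000 draws each. The log-scale SD is sqrt(ln(1 + CV²)).

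The lowest value can be checked by hand. With median 12, CV 0.15 and d = 5, the log SD is sqrt(ln 1.0225) = 0.149. The limits 10 and 15 seconds lie at z = −1.22 and z = 1.50, so P(10 ≤ X < 15) is about 0.933 − 0.111 = 0.822. The second interval adds almost nothing. The unchanged share is about 18%, as simulated.

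| Gain | Lognormal range | Lognormal scenarios below 50% | Uniform 5–30 s |
|---|---|---|---|
| 1 s | 76–99% | 0 of 27 | 92% |
| 2 s | 54–99% | 0 of 27 | 84% |
| 3 s | 39–99% | 2 of 27 | 76% |
| 5 s | 18–99% | 7 of 27 | 60% |

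For proportional improvements the lognormal ranges are 73–99% (10% faster), 46–99% (20%) and 23–99% (30%). The two scenarios below 50% at 3 seconds are medians of 11 and 12 with CV 0.15, where baselines cluster just above the 10-second cut. The share starting below 10 seconds runs from 0 to 99%.

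**The case against.** The case for leaving the plan alone has four parts.

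1. **The bands have meaning.** They are functional-independence classes and cite a published study of the test in frail elderly persons, which Protocol Appendix 11 also gives as its source. The objective concerns the ability to rise and walk, which these classes address. This stands, and it is why the bands should be kept. A reader might infer that the exploratory question cannot be answered at all. The documents do not support that: the summaries answer it at band resolution, and SAP 8.2.7 puts every assessment into listings.

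2. **The choice was disclosed.** A reader of Section 5 alone might infer a silent switch. The version 4 history shows a deliberate, recorded choice. What remains is that Section 5 and the history disagree.

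3. **The protocol sentence is generic.** It covers very different endpoints, ends with a qualifier on appropriateness, and the protocol leaves full methods to the SAP. SAP 10.5 also speaks of raw data and changes where appropriate, and the table shells are separate documents not available here. So a summary in seconds might still be produced. But the qualifier follows the grouping by visit and sequence, and the specific SAP entries, 8.2.29 and Table 12, point to bands only.

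4. **The consequence is small.** SAP 10.6 plans no comparison between sequences, and the test does not enter TIS, DOW or the multiplicity procedure. This stands in full.

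**Conclusion.** The discrepancy is real and minor. The protocol plans values and changes of a measurement made in seconds; the SAP analyses bands only, defines no display of movement between them, and declares no departure in Section 5. Changes within a band will therefore read as no change in the summaries.

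A reader might go further and conclude that most real changes will be hidden. The documents do not support that as a general statement, because it depends on a baseline distribution and a size of change they do not give. Under the assumed baselines it holds for gains of 1 to 2 seconds in every scenario tried and for 3 seconds in most. It fails for larger gains when baselines sit just above a cut point. Subjects may enter with little or no muscle weakness, which makes times below 10 seconds plausible for some, but no times are stated for that stratum.

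Sample size, power, alpha, and the primary and key secondary analyses are untouched.

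**What to change.** In SAP Table 12, give Timed Up and Go two summary types. The first is continuous: observed value and change from the reference visit in seconds, by visit and treatment sequence, as for the other continuous endpoints. The second is categorical: the three bands as an additional display, preferably with a shift table from the reference visit. Amend the sentence in 8.2.29 so that the bands supplement the seconds.

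If the sponsor prefers bands only, declare the departure from Protocol 10.4.4 in SAP Section 5 and define in 10.5 or 10.6 how change between bands will be shown.

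The cost is one table entry, a small wording change and one more standard descriptive table, plus the shift table if it is adopted. No new data are needed.

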## 8.3 Study Periods Relative to Treatment

Definitions of the start and end of periods and reference visits are presented in [Table 8](#) and [Table 9](#).

Note: If some of the core set measures assessed at the Baseline/Week 1 or the Week 25 visit were assessed after start of IMP at the respective visit but within 5 days after start, the core set measures will be considered baseline assessments or included in the TIS calculation for Week 25 or Week 53, respectively. All these cases will be presented during the BDRM. The same approach will be applied for all other data collected in eCOA data.

**Table 8: Periods and Reference Visits for Study Periods 1 and 2**

Period	Start of period	Reference visit of period	End of period a
For efficacy analysis (TIS):			
Week 1 – Week 25 (Week 1 - EOP1)	Start date and time of the first IMP infusion	Baseline (before infusion of IMP)	Week 25 (before infusion of IMP)
Week 25 – 53/Week 56 b (Week 25 - EOP2)	Start date and time of the first IMP infusion at Week 25	Baseline (before infusion of IMP)	Week 53 (before infusion of IMP)/Week 56
For efficacy analysis (all other endpoints):			
Week 1 – Week 25 (Week 1- EOP1)	Start date and time of the first IMP infusion	Baseline (before infusion of IMP)	Week 25 (before infusion of IMP)
Week 25 – Week 53/Week 56 b (Week 25 - EOP2)	Start date and time of the first IMP infusion at Week 25	Baseline (before infusion of IMP) Week 25 (before infusion of IMP)	Week 53 (before infusion of IMP)/Week 56
For safety analysis:			
Week 1 – Week 25	Start date and time of the first IMP infusion	Baseline (before infusion of IMP)	Week 25 (before infusion of IMP)

Period	Start of period	Reference visit of period	End of period a
(Week 1 - EOP1)			
Week 25 – Week 53/Week 56 b (Week 25 - EOP2)	Start date and time of the first IMP infusion at Week 25	Baseline (before infusion of IMP) Week 25 (before infusion of IMP)	Week 53 (before infusion of IMP)/Week 56
Week 1 – Week 53/Week 56 b (Week 1 - EOP2)	Start date and time of the first IMP infusion	Baseline (before infusion of IMP)	Week 53 (before infusion of IMP)/Week 56

a The end of the period is the listed visit or the last visit before / at withdrawal. For efficacy, the assessments within 7 days following the IMP discontinuation will be included in the analysis if no rescue medication was administered before the respective assessment (see Section 8.2.3). Efficacy assessments for subjects who withdraw from IMP for reasons related to the Ukraine war that are assessed more than 6 weeks after the last IMP administration will be set to missing (see Section 10.2).

b If subjects do not continue treatment after Week 53, an EOP2 Safety Follow-up Telephone Call will be conducted to assess the subject's safety status at Week 56 (or 4 weeks after the final infusion). No efficacy measures will be collected at Week 56.

**Table 9: Periods and Reference Visits for Study Period 3**

Period	Start of period	Reference visit of period	End of period a
Week 53 – EOP3	Start date and time of the first IMP infusion at Week 53	Week 53 (before infusion of IMP)	EOP3

a The end of the period is the listed visit or the last visit before / at withdrawal.

### 8.3.1 Study Time Periods for Adverse Events

Adverse events (AEs) with onset date/ time after start of first infusion of IMP are TEAEs. Assessment whether an AE is considered treatment-emergent, will take place after imputation of partially missing dates (see Section 8.1.2).

The TEAE analysis will be done for the periods and groups shown in Section 11. An AE will be counted for the analysis of a period if the onset of the event falls within the period. For the definition of start and end of the periods see [Table 8](#) and [Table 9](#).

### 8.3.2 Study Time Periods for Concomitant Medications

The following classification of concomitant medication related to start date and the end date of IMP will be applied. Each medication belongs to one of the following categories:

- Assign to 'Prior' if the medication end date is before the date of the first IMP infusion.
- Assign to 'Concomitant in Period 1' if the medication start date is at or before start of first IMP infusion at Week 25 or the medication start date is at or before the end of the last IMP infusion in Period 1 AND the medication end date is at or after start of first IMP infusion at Week 1.
- Assign to 'Concomitant in Period 2' if the medication start date is at or before start of first IMP infusion at Week 53 or the medication start date is at or before the end of the last IMP infusion in Period 2 AND the medication end date is at or after start of first IMP infusion at Week 25.
- Assign to 'Concomitant in Period 3' if the medication start date is at or before the end of last IMP infusion in Period 3 AND the medication end date is at or after start of first IMP infusion at Week 53.
- Assign to 'Post' if the medication start date is after the date of the last IMP infusion

If a start or stop date is partially missing, the imputation takes place before the classification of the medication in the categories above.

### 8.3.3 Study Time Periods for Medical History

Prior medical conditions are those which end before the start of first infusion of IMP. All other Medical History entries are Concomitant medical conditions, including those with missing end date.

## 8.4 Values of Potential Clinical Importance

Not applicable.

## 9 Study Population

Unless otherwise stated, all tables and listings in this section will be based on the mITT analysis set, and all summaries and data listings will use treatment labels as specified in Section [7.2](#).

### 9.1 Disposition of Subjects

The following summaries will be provided by treatment sequence, period and overall (if applicable). Summaries for subject and IMP status will also be provided for the subgroup of Japanese subjects:

- Subjects in each of the analysis sets described in Section [6](#).
- Subject status, including
  - subjects screened,
  - screen failures (including the reason),
  - subjects randomized,
  - completed IMP,
  - discontinued IMP (including the primary reason)
  - completed the study, and
  - withdrawals from the study (including the primary reason).
- IMP status, including
  - completed subjects,
  - prematurely discontinued subjects (including the primary reason).

Reasons for study withdrawal and IMP discontinuation will be presented in the order they are displayed in the electronic Case Report Form (eCRF).

The following listings will be provided:

- Subjects excluded from analysis sets by analysis set
  - Reasons for study withdrawal including the date of withdrawal
-

Precise selection of protocol deviations to identify subjects to exclude from the PP analysis set and the PK analysis set will be defined and documented in the minutes of the BDRM before unblinding the study for the primary data analysis (ICH E9) (see Section 2).

## 9.2 Protocol Deviations

The following summaries will be provided by treatment group:

- Inclusion and exclusion protocol deviations.
- All major protocol deviations including inclusion and exclusion, with each protocol deviation classified as ‘Deviation that requires exclusion from per-protocol analysis set’ and as ‘Deviation that requires exclusion from PK analysis set’.

The following listings will be provided:

- All inclusion and exclusion protocol deviations.
- All other protocol deviations

## 9.3 Demographic and Baseline Characteristics

All demographic and Baseline characteristics summaries will be based on the mITT, PP, mITT-Ex, and PK analysis sets and the SAF-P3 for Study Period 3. They will be presented in summary tables by treatment sequence. Continuous data will be summarized by descriptive statistics and categorical data will be summarized by frequency distributions. Age will be described as both a continuous and a discrete variable. By-subject listings will be provided for demographic and Baseline characteristic data.

The following summaries will be provided by treatment sequence and overall. These summaries will also be provided for the subgroup of Japanese subjects in the mITT analysis set:

- Demographic characteristics
    - Age (years)
    - Age group (18-64,  $\geq$  65 years)
    - Sex
    - Ethnicity
    - Race and racial combinations
    - Body weight, baseline assessment (kg)
-

- Height (cm)
- BMI, baseline assessment (kg/m^2)
- Prior IgG treatment (identified by ATC 3 =“IMMUNOGLOBULINS”)
- Disease characteristics at Screening
- Prior medical conditions
- Concomitant medical conditions

The following summaries of the number and percentage of subjects in each stratum will be provided:

- Region (Japan vs. non-Japan)
- Baseline MMT-8 ( $\leq$  142 points vs.  $>$  142 points)

The following listings will be provided:

- Demographic characteristics
- Race and racial characteristics
- Disease characteristics at Screening
- Prior and concomitant medical conditions

## 9.4 Prior and Concomitant Medications

Prior and concomitant medications will be coded using WHO Drug Dictionary Enhanced (WHO-DDE) 2018 Mar B3 or more recent version, summarized, and listed. The summary of concomitant medications will show the number and percentage of subjects taking prior and concomitant medications. Anatomical Therapeutic Chemical (ATC) classification Level 1 (Body System) information will be included in the data set created but will not appear on the listing or summary.

In the summary of concomitant medications, each subject is counted once within each unique term. For example, if a subject takes Amoxicillin on two separate occasions, the subject is counted only once under the ingredient “Amoxycillin”.

---

Summaries for the following categories will be provided:

- Prior Medication (including corticosteroids) for mITT
- Concomitant Medication (including corticosteroids) for mITT, mITT-EX and for SAF-P3
- Prior Medication (including corticosteroids) to Treat Dermatomyositis for mITT
- Concomitant Medication to Treat Dermatomyositis, excluding Oral Corticosteroids for mITT and mITT-EX
- Oral Rescue Corticosteroid Treatment for mITT
- Oral Concomitant Corticosteroid Treatment, Excluding Oral Rescue Treatment for mITT

## 9.5 Non-Pharmacological Interventions and Physiotherapy

A listing for non-pharmacological interventions, physiotherapy, and change of physiotherapy will be provided.

## 10 Efficacy

This section describes the planned analyses of efficacy endpoints. mITT will be the primary analysis set for the analysis of all efficacy endpoints. PP will be the supportive analysis set for the primary and key secondary efficacy endpoint.

### 10.1 Primary Estimand

The primary interest is to quantify the treatment effect of IgPro20

- where the potential confounding effect of oral rescue corticosteroid treatment is excluded
- where the potential confounding of subjects who withdraw from treatment or the study before Week 25 and cannot provide sufficient data to demonstrate a benefit of treatment is excluded, and
- in the absence of premature withdrawal from IMP or the study before Week 25 due to the Ukraine war [[EMA Biostatistics Working Party, 2022](#); [ICH E9 \(R1\), 2020](#)].

The primary estimand in line with the primary interest of the study is described as follows:

- Population: the target patient population defined by eligibility criteria and who received any amount of randomized IMP and have post baseline efficacy results in Study Period 1 (mITT). See Section 6 for details.
- Variable: responder status based on TIS assessments at Weeks 17, 21, and 25
- Intercurrent events:
  - withdrawal from randomized IMP or the study, which is not related to the Ukraine war, or receiving oral rescue corticosteroid treatment before Week 25 is considered treatment failure
  - withdrawal from randomized IMP or the study which is related to the Ukraine war will be addressed using the hypothetical strategy [Meyer et al, 2020; Collins et al, 2020].
- Population-level summary: responder rate by treatment sequence

